
Table 1. List of variables extracted from electronic medical record data.

Observed Independent Variables	
Demographics	Age, gender, race/ethnicity, marital status, service connected disability.
Non-psychiatric illness	Elixhauser measure
Depression diagnoses	ICD-9 Depression Codes e.g., 296.2-296.36; 293.83; 309.0.
Anxiety Disorders/ PTSD diagnoses	ICD-9 CM codes for Anxiety and Stress-related conditions e.g., 293.84; 309.24; 309.28; 309.81; 300.00-300.09.
Serious Mental Illness diagnoses	ICD9-CM codes for Bipolar Affective Disorder Type 1, Schizophrenia e.g., 293.81-293.83; 296.40-296.7; 295.40-295.90; 296.56-293.83.

Alcohol/Substance Use Disorder Diagnoses	ICD9-CM codes for Alcohol, Amphetamine, Cocaine, Inhalant Use Disorders: 291.89-304.40.
Depression severity	PHQ-9 items and scores
Depression chronicity	Time from first to last ICD9 code or time between elevated PHQ9s
Anxiety severity	GAD-7 items and scores
PTSD severity	PCL-5 items and scores
Affective characteristics	PCL-5 clusters C (emotional avoidance), D (negative mood and cognitions), E (arousal and reactivity)
Somatic difficulties	Somatic factor of the PHQ9 (e.g., fatigue, sleeping difficulties)
Instrumental Variables	
Distance to the VA	e.g., GIS tracking, zip code mapping
System approachability	Is the mandatory annual depression screen completed in the past year?; Does pt have PCMH routine check in over the past two years?
Ability to reach VA	Has available transportation/eligible for VA transportation; full time or multiple jobs
Family support	Asian and Black race (as proxy) have been associated with increased social stigma of mental illness, including lack of family/friends support to seek mental health services
Beliefs about care	Gender and race have been associated beliefs about MH care
Unobserved Variables	
Transportation availability	These variables have been repeatedly identified in the literature as barriers to mental health treatment. We will not have this information available in the structured data.
Employment	
Child or family care	
Outcome Measure (Dependent Variable)	

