Treatment initiation	A primary or secondary stop code showing a visit in mental health (with a psychologist or psychiatrist) or primary care AND an ICD9 for depression diagnosis.

Sampling plan and data extraction and processing:

**Data source and cohort selection.** We will use data from the VA Corporate Data Warehouse (CDW), a centralized data repository which contains electronic medical records of all Veteran patients who receive care through the VHA. The patient cohort (N = 88,456) used for completion of Aim 1 includes 1) OEF/OIF Veteran patients with a PHQ9  $\geq$ , 2) who were not already in treatment for depression prior to this PHQ9 assessment, 3) were never diagnosed with bipolar, personality, psychotic, and pervasive developmental disorders to be consistent with the National Committee on Quality Assurance measure of quality of care, HEDIS (HEDIS, 2018), as well as substance dependence or patients who are in treatment for substance related disorders at the time of recruitment. The exclusion criteria are based on the fact that the presence of these disorders may result in divergent treatment practices compared to unipolar depression in the absence of these conditions. Our primary outcome, treatment initiation, is conceptualized as a combination of service encounters with specialty mental health (psychologists, psychiatrists) or primary care providers charted into the patients' VHA medical records (excluding assessments) that were associated with any depressive disorder diagnosis. Our data are already IRB exempt, R&D and DART approved, and have already been extracted.

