**Data processing.** Data will be initially checked for out of range values and missing data where appropriate through plotting and descriptive analyses. Data will be transformed as needed. Logistic regression is relatively free of restrictions and can accommodate a mix of predictors (continuous, discrete, dichotomous) (Tabachnick & Fidell, 2007). *With continuous predictors, the assumption is that there is a monotonic relationship (increase or decrease) between the predictor variable and odds of the binary outcome (i.e. engagement or lack of engagement in care). The functional of this linear assumption can be evaluated by use categorical indicator variables as well as transformations of the continuous variable, such as a quadratic form. Multicollinearity will be tested using two approaches. First, we will explore correlations among IVs and exclude variables based on high correlations ( $> .65$ ). Second, we will examine the size of the standard error (SEs) relative to the beta coefficient for each predictor in the model. Large SEs will be indicative of potential multicollinearity. Residuals will be tested to identify possible outliers.*

Analysis plan:

**Modeling risk for lack of treatment engagement.** For all analyses, lack of treatment engagement is the main dependent variable and will be investigated using three related definitions based on the date in which a PHQ9 score  $\geq 10$  is identified in the EHR. Specifically, we will examine whether treatment is initiated within 3-months, 6-months, or 12-months from the date of the PHQ9 assessment. *Independent variables of interest will be extracted based on proposed framework, empirical evidence, and availability in the EHR (see Table 1), including insight from a select number of semi structured surveys collected prior to data analysis (described below).*

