*Fortunately, the EHR is rich in terms of wealth of potential predictors to carry out the analyses. This work is a first step in the development of an automated system that can be implemented in the VHA EHR to more easily identify patients who may be in need but at risk for lack of engagement in mental health treatment.* A direct logistic regression will be performed to evaluate the battery of proposed and potential factors as possible predictors of lack of treatment engagement. The final model will be estimated using the validation sample (half of our overall available sample). Regression (beta) coefficients and odds ratios will be extracted for interpretation and evaluation of risk to not engage in treatment in our next step.

*Computation of health service utilization risk score.* Using coefficients extracted from final logistic regression testing the best fitting patient phenotype associated with lack of treatment engagement, we will compute a risk score for lack of treatment engagement. This score will be used to select high risk patients enrolled in our intervention development and evaluation studies (Aims 2 and 3). The logistic regression equation will be used to calculate the risk scores using the intercept and co-variated specific coefficients that relate to the probability of lack of treatment initiation. Therefore, the equation will be based on the logistic regression model which will be developed in the log odds scale.

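### The second multicollinearity check in Aim 1 (each SE against its own beta) is the inverse of the Wald statistic, so it confounds collinearity with effect size and sample size; VIF and condition indices should replace it

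*Protocol*

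**What the plan says.** Section A4a of the protocol, under Data processing, plans two tests for multicollinearity in the Aim 1 logistic regression.

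- The first is pairwise: "First, we will explore correlations among IVs and exclude variables based on high correlations", with the threshold set at .65. (Here IVs means independent variables.)
- The second looks at the size of each standard error "relative to the beta coefficient for each predictor in the model. Large SEs will be indicative of potential multicollinearity". It has no numerical cut-off, and no action follows from it.

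Neither the protocol nor the SAP mentions variance inflation factors, tolerance or condition indices.

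The results are meant to be read predictor by predictor. Under the Analysis plan in A4a, "Regression (beta) coefficients and odds ratios will be extracted for interpretation and evaluation of risk to not engage in treatment". The same coefficients then form the risk score used to select patients for Aims 2 and 3.

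Table 1 lists overlapping candidates. Depression severity is entered as "PHQ-9 items and scores", and a somatic factor of the same questionnaire appears separately. GAD-7 is listed as items and scores. PCL-5 is listed as items and scores, with clusters C, D and E again as affective characteristics.

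**The concern.** Whether a predictor is collinear depends only on the predictors. The ratio of a standard error to its own coefficient also depends on how strongly that predictor relates to the outcome and on the number of patients. It can therefore be large with no collinearity at all, because the effect is weak, and small despite marked collinearity, because the effect is moderate and the sample is large.

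This matters because of what the first check cannot see. A pairwise screen misses a predictor that is nearly a combination of several others when no single correlation is high. Of the two named tests, only the second could detect that, and questionnaire items alongside their totals, factors and clusters are where it would arise. At stake is the reading of individual odds ratios: which predictors are labelled as entangled, and which are read as separate effects when they should be read together.

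**Working it through.** The plan states no figure for this check, so there is none to reproduce.

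**Inputs from the documents.** The cohort is 88,456, and "The final model will be estimated using the validation sample (half of our overall available sample"), so n = 88,456 / 2 = 44,228. The pairwise threshold is .65.

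**Assumptions.** The documents give no initiation rate for the Aim 1 cohort. I use p = 0.185 and 0.27, the ends of the utilization range in A1, and 0.5 as a bound. Cut-offs of 0.5 and 1 for the ratio, and all effect sizes (per SD), are mine.

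**Step 1: what the ratio is.** Wald z = beta / SE, so SE/|beta| = 1/|z|. A cut-off of 0.5 is the rule |z| < 2; a cut-off of 1 is |z| < 1. For a predictor with no effect and no correlation with the others, P(|z| < 2) = 0.954 and P(|z| < 1) = 0.683. Simulated logistic regressions with five independent predictors (300 runs per outcome rate) gave 94–95% and 63–67%.

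**Step 2: size at this n.** For a standardized predictor, SE is approximately sqrt(VIF / (n p(1 − p))). The term n p(1 − p) is 6,668 at p = 0.185, 8,717 at 0.27 and 11,057 at 0.5.

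| Predictor | p = 0.185 | p = 0.27 | p = 0.5 |
|---|---|---|---|
| VIF 1, beta 0.005 | 2.45 | 2.14 | 1.90 |
| VIF 10, beta 0.3 | 0.13 | 0.11 | 0.10 |
| VIF 50, beta 0.3 | 0.29 | 0.25 | 0.22 |
| VIF 100, beta 0.3 | 0.41 | 0.36 | 0.32 |
| VIF 100, beta 0.1 | 1.22 | 1.07 | 0.95 |

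The order is reversed: the predictor with no collinearity has the largest ratio. With beta 0.3, the ratio reaches 0.5 only when VIF = (0.5 × 0.3)² × n p(1 − p) = 0.0225 × 6,668 to 0.0225 × 11,057, that is about 150 to 249.

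**Step 3: what the first check leaves.** For two predictors, r = .65 gives VIF = 1 / (1 − 0.4225) = 1.73, so the screen is strict for pairs. What remains is dependence among three or more variables.

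**Step 4: simulation of that gap.** A fifth predictor was built as nearly the sum of four independent ones, with betas 0.2, 0.2, 0.2, 0.2 and 0.3, n = 44,228, and non-engagement of 73% or 81.5% (that is, 1 − 0.27 and 1 − 0.185). Pairwise correlations were about .5, so the screen passed them all. With a cut-off of 0.5:

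- VIF 10 and 20: the fifth predictor was flagged in 0% of runs.
- VIF 50: it was flagged in 3.5% to 7.5% of runs, across two sets of 200 runs per case.
- VIF 200: at least one of the five predictors was flagged in 88% to 100% of runs.

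**Step 5: a questionnaire-like case.** Nine items with inter-item correlation .30, a near-total score, and one independent weak predictor (beta 0.005) were fitted once at each outcome rate. All pairwise |r| were at most .62. The near-total score had VIF of about 101 and ratios of 0.20 to 0.31. The independent predictor had VIF 1.0 and ratios of 1.0 to 2.9, the largest in every run. VIF ranked the predictors correctly.

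**Step 6: consequence.** In the Step 4 setting, the fifth coefficient averaged about 0.28 to 0.31 at VIF 10 and 20 (true value 0.30), with SE 0.035 to 0.057. Fitted and true linear predictors correlated at least 0.997 at every VIF tried, including 200.

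**The case against.** The strongest case for leaving the text alone is that the misses do little harm. At VIF 10 to 20 the coefficients are essentially unbiased and precise enough to use, because the sample is large. Where collinearity becomes severe, the ratio does rise. This stands, and it limits the size of the point. It does not make the ratio a collinearity diagnostic: a low value does not show that a predictor is free of dependence, and a high one does not show that it is collinear.

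It can also be said that a flag has no consequence. That stands too: exclusion is tied only to the pairwise screen, and the wording speaks of potential multicollinearity. A reader might infer that weak but harmless predictors will be dropped; the documents do not say so.

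Other parts of A4a help. Lasso, trees and random forests are compared on variable importance and interpretability, and variation across the ten cross-validation models is examined. These bear on stability but do not say which predictors are jointly dependent. Table 1 lists extracted variables and is not a final model specification, and an exact item-sum dependence would show itself as a model that cannot be estimated. Near-dependence would not.

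Taking large SEs in absolute terms does not rescue the check, since an SE depends on each predictor's scale.

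Two stronger readings are tempting. One is that collinearity goes unchecked; it does not, because the .65 screen is strict for pairs. The other is that the risk score, and so the choice of Aim 2 and 3 patients, is compromised. Nothing in the documents shows this, and the simulated scores were almost unchanged.

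**Conclusion.** The point holds in a limited form. The identity with 1/|Wald z| is exact and needs no assumption. At n of about 44,000 the second check marks uncorrelated weak predictors as potentially collinear, and does not register dependence among three or more moderately strong predictors at VIF 10 to 20, and mostly not at 50, when all pairwise correlations pass .65.

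The harm is confined to labelling and interpreting individual odds ratios. Effects on the risk score and on Aim 2 and 3 selection are small. The SAP contains no Aim 1 logistic model, so no Aim 3 estimate in it uses this check.

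The flag rates rest on assumed cut-offs, outcome rates and effect sizes. A smaller beta at the same VIF would be flagged more readily, as the last row of the table shows. The ranking of predictors in Step 5 was the same at all three outcome rates. The change is worth making because the rule as written gives wrong diagnoses and the remedy is nearly free.

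**What to change.** In A4a, Data processing, replace the second approach with:

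> Second, we will compute variance inflation factors (generalised VIF for categorical predictors) and condition indices from the design matrix. Sets of predictors with high values (e.g. VIF > 10) will be reported and reviewed, and their individual odds ratios interpreted jointly or the set combined where interpretation requires it. The SE-to-beta ratio will not be used to diagnose multicollinearity.

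VIF > 10 should serve as a flag for review and should not trigger automatic removal, since predictors at VIF 10 to 20 were well estimated at this sample size and may be useful for prediction.

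The cost is a short text change and a line of code on data that the protocol says are already extracted. No new patients or data are needed. The small downside is having to choose a conventional flagging threshold.

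### The second multicollinearity check (standard error relative to beta) measures Wald significance, so it cannot tell collinear predictors from weak ones, and the pairwise screen covers only part of the gap

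*Protocol*

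**What the plan says.** Protocol section A4a (Aim 1), under Data processing, states that "Multicollinearity will be tested using two approaches". The first is a correlation screen: "First, we will explore correlations among IVs and exclude variables based on high correlations", with a cut-off of .65. The second is that "we will examine the size of the standard error (SEs) relative to the beta coefficient for each predictor in the model", followed by the reading that "Large SEs will be indicative of potential multicollinearity". No threshold for a large value is given, and no VIF, tolerance or condition index is named.

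Table 1 in the same section lists overlapping measures. For depression severity it has "PHQ-9 items and scores", with a PHQ-9 somatic factor as a further row. GAD-7 and PCL-5 are also listed as both items and scores, and PCL-5 clusters C, D and E appear separately.

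Under Analysis plan, the betas and odds ratios are to be interpreted and then used to compute the risk score that selects patients for Aims 2 and 3. The SAP does not cover the Aim 1 model.

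**The concern.** A collinearity diagnostic should respond to how well a predictor is explained by the other predictors. Dividing the standard error by the coefficient brings in the size of the effect. The ratio is then large when the effect is near zero, whatever the correlation structure, and small when the effect is clear and the sample is large, even under strong collinearity.

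What is at stake is the reading of individual coefficients. Aim 1 describes a phenotype, that is, which patient characteristics matter and by how much. If related scores share an effect, the split between them is less certain than it would be for unrelated predictors, and the planned check may not say so. A weak but unrelated predictor may be reported as a collinearity problem.

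**Working it through.** **Inputs from the protocol.** Cohort: "The patient cohort (N = 88,456) used for completion of Aim 1". Estimation sample: "The final model will be estimated using the validation sample (half of our overall available sample"), so n = 88,456 / 2 = 44,228. Correlation cut-off: .65. The protocol gives no figure for the second check, so there is nothing to reproduce.

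**Assumptions, not in the documents.** Outcome rate p from 20% to 50%; odds ratio 1.3 per SD as an example of a real effect; a ratio above 0.5 (|z| below 2) as an example of a large value.

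**Step 1, identity.** z = beta / SE, so SE / |beta| = 1 / |z|. In the simulated logistic fits that printed both quantities, they agreed for every coefficient.

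**Step 2, weak but independent predictor.** With beta = 0 and VIF = 1, P(SE/|beta| > 0.5) = P(|z| < 2) = 2Φ(2) − 1 = 0.954, at any sample size.

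**Step 3, collinear predictor with a real effect.** For a predictor scaled to 1 SD, approximately SE = sqrt(VIF / (n p (1 − p))). Here ln 1.3 = 0.2624.

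| p | n p (1 − p) | SE at VIF 10 | SE/beta at VIF 10 | SE at VIF 20 | SE/beta at VIF 20 |
|---|---|---|---|---|---|
| 0.20 | 7,076 | 0.0376 | 0.143 | 0.0532 | 0.203 |
| 0.50 | 11,057 | 0.0301 | 0.115 | 0.0425 | 0.162 |

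For the ratio to reach 0.5, VIF would have to be (0.5 × 0.2624)² × n p (1 − p), which is about 122 at p = 0.20 and 190 at p = 0.50.

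**Step 4, when the ratio does respond.** It grows with sqrt(VIF). Two predictors with r = .95 (VIF 10.3) were simulated 50 times per setting at n = 44,228, with an outcome rate of about 27% when effects are small:

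- both betas 0.3: flagged in 0% of runs;
- both betas 0.05: flagged in 72% and 76%;
- both betas 0.02: flagged in 90%;
- betas 0.3 and 0: the redundant member flagged in 92%, its partner in 0%.

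Whether a collinear predictor is flagged therefore depends on its effect size.

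**Step 5, what the first screen covers.** It removes the r = .95 pairs, and it is strict for pairs: at r = .65, VIF = 1 / (1 − .65²) = 1.73. It does not see dependence spread over several variables. In a simulated model, one predictor was nearly the sum of four uncorrelated others. Its VIF was 12.3, yet its largest pairwise correlation was 0.48, so it passes the screen. Its SE/|beta| was 0.16 (20% outcome rate) or 0.11 (50%), so it passes the second check too. In the same fits, an independent predictor with true beta 0.005 and VIF 1.0 had a ratio of 26.0 or 0.64.

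**Step 6, closer to Table 1.** The cohort is restricted to PHQ-9 of 10 or more, which lowers item-total correlations. Nine items scored 0 to 3 were simulated from one factor (assumed loadings 0.6 to 0.8, two sets of thresholds), keeping totals of at least 10. The highest item-total correlation was 0.38 to 0.58 and the highest inter-item correlation at most 0.26. All nine items and the total pass the .65 screen, although the intercept, items and total together are exactly dependent (rank 10 of 11 columns).

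**The case against.** Several points on the other side are sound.

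**No removal rule attaches to the second check.** A reader might infer that predictors will be dropped because SE/beta is large. The text does not say so: exclusion belongs only to the first screen, and the second is described as indicative. Dropping predictors on this ratio is a risk of the wording, not a stated step.

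**The check does not fail on collinear predictors in general.** Step 4 shows that weak or redundant collinear predictors are often flagged. Those that pass have clear effects.

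**The example coefficient is still precise.** At VIF 10 and p = 0.20, the 95% interval for the odds ratio is exp(0.2624 ± 1.96 × 0.0376), or 1.21 to 1.40. Missing it does little harm in that instance. This supports a low priority but does not make the ratio a collinearity diagnostic.

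**The pairwise screen may catch many item-total overlaps.** With equal variances and a common inter-item correlation, an item correlates above .65 with its total once the inter-item correlation exceeds (0.4225k − 1)/(k − 1). That is about .35 for the nine PHQ-9 items and .39 for the 20 PCL-5 items. The documents give no correlations, so coverage cannot be settled either way. Step 6 shows that escape is plausible in this restricted cohort.

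**Table 1 lists extracted variables, not model terms.** A reader might infer that items and totals will be fitted together. Nothing says that they will, and an exact dependence would show itself as a singular fit or a dropped term. Nothing rules joint entry out either, and near-exact overlap would not announce itself in that way.

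**Conclusion.** The point holds as a minor one. The second check is 1/|z| and cannot distinguish collinearity from a weak effect. At n = 44,228 it can pass a predictor with VIF 10 and odds ratio 1.3 per SD (ratio 0.115 to 0.143), while an independent null predictor exceeds 0.5 in 95% of samples. The first figure rests on the assumed outcome rate of 20% to 50% and the assumed effect size; the second needs neither. Both use 0.5 only as an illustrative cut.

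Beyond the pairwise screen, the plan has no valid diagnostic for dependence among several variables, and Table 1 contains candidates for it. The consequence is mainly for interpreting coefficients and odds ratios as a phenotype. Prediction from the combined score is much less affected, and the documents do not support a claim that the score used to select patients would be wrong.

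**What to change.** In A4a, Data processing, replace the SE-relative-to-beta check with VIFs or condition indices computed on the predictor matrix, with a stated threshold and a statement of what will be done when it is exceeded. Beside Table 1, state that for PHQ-9, GAD-7 and PCL-5 either the items or the totals and clusters will enter a given model, not both. The choice between conventional logistic regression and Lasso can stay with the comparison already planned for Stage 2.

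The cost is one or two sentences and a standard software option. No new data are needed.
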